## **Interventions**

Participants in the intervention group will receive a collaborative stepped care programme provided by registered social workers and trained Peer Supporters from elderly service units, the Districts Elderly Community Centres (DECC), and mental

health service units, the Integrated Community Centre on Mental Wellness (ICCMW), all local NGOs. In the collaborative stepped care model (see Table 1), older persons are matched to the intervention module that most suits their current needs. The person does not have to start at the lowest level of intervention to progress to the next level of intervention. Rather, they enter the service with the intervention level aligned to their needs, e.g., level of risks, symptom severity (measured by the Patient Health Questionnaire, PHQ-9), and intervention response. Home visits or other format of contact will be delivered by trained Peer supporters employed by the NGOs to detect and engage hidden cases.

Table 1. JoyAge Collaborative Stepped-Care Service

	Indicated Prevention for Mild Symptoms	Clinical Intervention for Moderate Symptoms	Intensive Clinical Intervention for Moderately Severe Symptoms
Intervention goal	To reduce depressive symptom level to normal level, enhance resilience	To reduce depressive symptom level to mild depression or below	To reduce depressive symptom level to moderate depression or below
Key intervention mode	Psychoeducation on a specific topic (insomnia, pain, stress, and anxiety), or low-intensity psychotherapy	High-intensity psychotherapy	High-intensity psychotherapy
Principal team	DECC	DECC and ICCMW	ICCMW

For older adults with mild depressive symptoms (PHQ-9 score 5-9), 6-8 weeks of indicated prevention with psychoeducation or low-intensity psychotherapy would be provided by the project social workers in the DECC. For participants with moderate symptoms (PHQ-9 score 10-14), 6-8 weeks high-intensity clinical intervention, mainly cognitive behavioral therapy (CBT), would be provided by project social workers from the DECC and ICCMW. For those with moderately severe depressive symptoms, individual CBT or group CBT at higher frequency would be provided by the project social workers from the ICCMW.

Participants should be stepped up to clinical intervention at a more intense level if they showed increased level of depressive symptoms after receiving one rounds of services,

and stepped down to lower level if they showed improvements. Participants showing severe depressive symptoms or increased suicide risk should be referred out to other appropriate services. In the review session after completion of the intervention, when a person is assessed to be meeting the discharge criteria, a 2-month Exit Plan involving a Peer Supporter follow-up should be invoked. The key social worker will work with the client to develop a 6- to 8-week Mental Health Wellness Plan (e.g., activity scheduling) to further improve or consolidate the protective factors.

All intervention would be conducted by registered social workers who are trained by this project and employed by the NGOs. The trained Peer Supporters will be matched to individual older adults to walk them through the process with regular follow-up until discharged or referred out.

## Measurements

Basic demographics including age, gender, marital status, education (years and highest attainment), and work experience will be collected at T0. At following time points, only updates of the basic demographics will be recorded. At both T0 and T1, a full set of assessment will be conducted; and at T2, only the primary outcomes would be measured. *Primary outcomes* 

- 1. Depression: The Patient Health Questionnaire (PHQ-9) (Kroenke, Spitzer, & Williams, 2001): a 9-item instrument that incorporates depression diagnostic criteria with other leading major depressive symptoms, and rates the frequency of the symptoms which factors into the scoring severity index. PHQ-9 scores of 5-9, 10-14, 15-19, 20 and above represent mild, moderate, moderately severe, and severe depression.
- 2. Anxiety: Generalized Anxiety Disorder 7-item scale (GAD-7) (Spitzer, Kroenke, Williams, & Löwe, 2006), a 7-item scale, responses to each item are rated on a 4-point Likert scale and range from 0 to 3. It taps on the most prominent diagnostic features for GAD and scores of 5, 10, and 15 are taken as the cut off points for mild, moderate, and severe anxiety, respectively.
- 3. Loneliness: UCLA loneliness scale (UCLA-3) (Hughes, Waite, Hawkley, & Cacioppo, 2004), a 3-item self-report measuring individual's perceived loneliness. Each item is evaluated with scores ranging from 0 (never) to 3 (often), total score

- is the sum of all items, and higher score indicates higher level of perceived loneliness.
- 4. Self-harm risk assessment: Assessment by social service staff on participant's risk of self-harm (yes or no answers to 10 items) and harm to others (yes or no answers to 4 items), and in the end social service staff will give an overall evaluation of suicidal risk score ranging from 0-No to 3-High.
- 5. Wellbeing quality of life: EQ-5D-5L (Herdman et al., 2011), a generic preference-based measure of health at five dimensions (5D), each with five levels (5L) of problems, and the five dimensions are: mobility, self-care, usual activities, pain/discomfort, and anxiety/depression. The traditional Chinese version for Hong Kong developed by EuroQol Group would be used.
- 6. Personal recovery: Recovery Assessment Scale (RAS), validated Chinese version (Mak, Chan, & Yau, 2016), a 24-item RAS assesses personal recovery, specifically focusing on self-determination and hope as the major areas of recovery. Items are rated on a five-point likert scale. For the purpose of this study, only the five items from the "Goal and success orientation" factor would be included.
- 7. Treatment and recovery goal: Self-developed questionnaire asking about present, anticipated, and desired personal best in personal recovery goal, social network, and activities to participate in the community.
- 8. Health care expenditures: Client Service Receipt Inventory (CSRI) (Chisholm et al., 2000), to collect the current types and level of social services which comprise the care package of each participant, and a locally adapted short version would be developed for this purpose. Based on the localized health utilities and duration, we will further calculate the QALYs. The service utilization data will be obtained from Health Authority, covering information on outpatient visits, hospitalization days, Accident and Emergency service utilization, types of medications and operations, other diagnoses, self-harm, and any other major cost items that may be affected by depression with cost implications.

7

<sup>1 Separate application has been submitted to Hospital Authority (HA) Institutional Review Board for HA data use.

#### Secondary outcomes

- 1. Lifestyle: Typical Day, a semi-structured interview asking clients about their typical day activities in three domains, physical, social, and mental. A combination of being active in at least two domains would be used as one of the exit criteria.
- 2. Cognition: Hong Kong Montreal Cognitive Assessment 5-Minute Protocol (HK-MoCA 5-Min) (Wong et al., 2015), a validated and reliable cognitive screen for stroke and transient ischemic attack. It includes four items examining attention, verbal learning and memory, executive functions/language, and orientation extracted from the MoCA.
- 3. Support network: asking participants to list out names of people who they would turn to when they feel down, and when they need help for trivial things.
- 4. Perceived environment: Self-developed questions of perceived residential environment derived from sense of community scale (McMillan & Chavis, 1986) and neighbourhood environment walkability scale (Saelens, Sallis, Black, & Chen, 2002).
- 5. Pain management: Using Chronic pain acceptance questionnaire (CPAQ-8) (Fish, McGuire, Hogan, Morrison, & Stewart, 2010), participants will rate the extent to which the eight statements about pain acceptance are true for them on a 7-point Likert scale, and higher scores indicates greater levels of acceptance.

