# **Objectives**

- a) To implement JC JoyAge clinical protocol and guidelines to coordinate care among community mental health and elderly services centres for elderly mental wellness in 18 districts;
- b) To engage vulnerable and at-risk older adults in the community through productive ageing activities and mental wellbeing self-management training;
- c) To enhance the capacity of social service staff in handling elderly depression through specialized and *infusion* training and knowledge exchange;
- d) To raise public awareness and elderly mental health literacy among family members, neighbours, community stakeholders, and the general public to encourage early detection/help-seeking on depressive risk of older adults; and
- e) To establish evidence of the effectiveness and cost-effectiveness of JC JoyAge Phase II model.

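### The support-network outcome does not separate people the programme supplies from the participant's own contacts, so a gain at T1 may reflect receipt of the service

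*Combined protocol and SAP*

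**What the plan says.** Under Secondary outcomes, support network is obtained by asking participants to "list out names of people who they would turn to when they feel down, and when they need help" with minor matters. Nothing further is said: no scoring rule, no record of who each named person is to the participant, and no statement on whether programme staff qualify.

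Under Interventions, Peer Supporters are to be "matched to individual older adults to walk them through the process with regular follow-up until discharged or referred out". Under Assessment Procedures, a social worker carries out T1 after the intervention has been completed or the participant has dropped out, and the decision to discharge is taken on the T1 findings. Dischargeable clients then enter a 2-month exit period, again with Peer Supporter follow-up, and Peer Supporters carry out the T2 assessment.

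The Design section describes a single-arm, open-label, pre-post study. The full set of measures is taken at T0 and T1, but "at T2, only the primary outcomes would be measured", so support network has two time points. Data Analysis names methods for the main outcomes only, although it promises effect sizes, significance and confidence intervals for all results.

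Typical Day, another secondary outcome, is "a semi-structured interview asking clients about their typical day activities in three domains, physical, social, and mental". No rule says how activities delivered by the programme are treated. Its one stated use is at domain level: "A combination of being active in at least two domains would be used as one of the exit criteria".

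**The concern.** A question about whom one would turn to invites the participant to name the Peer Supporter. That is a truthful answer, because the programme has assigned a person for that kind of support and the contact is still running at T1. As a matched relationship it does not exist at T0. The list can therefore lengthen, or change in composition, without any change in the participant's own network.

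At stake is the meaning of a reported improvement in social support. In a controlled trial, a comparison group might show how far such a change comes from the service itself. Here there is no comparison group, and if the names are not labelled when they are collected, the two sources cannot be separated afterwards.

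Typical Day raises a milder form of the same question. Programme contact or programme activities could be reported as social or mental activity, and the plan does not say whether they should be.

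**Working it through.** The plan states no figure for this outcome, and no SD, expected change, alpha, power or dropout rate, so there is nothing to reproduce. The check has two parts.

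**1. The passages side by side**

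- Who may be named: anyone the participant would turn to (Secondary outcomes). No section restricts this.
- Whom the programme supplies: a matched Peer Supporter, with follow-up until discharge or referral out (Interventions).
- When the list is taken: T0 and T1 (Measurements). Discharge is decided on the T1 findings (Assessment Procedures), so the follow-up has not ended when the T1 list is taken from someone not yet discharged or referred.
- What could separate the two sources: a comparator (none, under Design) or a label on each name (none described).

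The gap in the definition follows from the text without any arithmetic.

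**2. How few participants would be needed (illustration only)**

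Input from the documents: n = 3,000 (Participants).

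Assumptions, not in the documents: the outcome is summarised as a number of names; the SD of the T0 to T1 change is 1.0, 1.5 or 2.0 names; either all 3,000 or 2,100 (30% loss) complete T1; a share f of participants adds exactly one name, the Peer Supporter's, and nothing else changes on average; the test is a two-sided paired comparison at 0.05.

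The mean gain is then f names. The share giving 80% power is

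f = (1.960 + 0.842) × SD / √n = 2.802 × SD / √n.

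For n = 3,000, √n = 54.77 and 2.802 / 54.77 = 0.0511. For n = 2,100, √n = 45.83 and 2.802 / 45.83 = 0.0611.

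| SD of change | f, 3,000 completers | f, 2,100 completers |
|---|---|---|
| 1.0 | 5.1% | 6.1% |
| 1.5 | 7.7% | 9.2% |
| 2.0 | 10.2% | 12.2% |

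The standardised change at these thresholds is f / SD, which is 0.051 with 3,000 completers and 0.061 with 2,100, whatever the SD.

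The formula leaves out the variance that the naming itself adds. With it included, z = f√n / √(SD² + f(1 − f)):

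- f = 5%, SD 1.0, n = 3,000: z = 2.68, power 0.76.
- f = 10%, SD 2.0, n = 3,000: z = 2.71, power 0.77.
- f = 20%, n = 3,000: z = 10.2 (SD 1.0) to 5.4 (SD 2.0), standardised change 0.19 to 0.10.
- f = 20%, n = 2,100: z = 8.5 to 4.5, same standardised changes.

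The thresholds therefore move only slightly. If programme-supplied names are left out of the outcome, this contribution is zero by construction.

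**The case against.** The strongest objections limit the point without removing it.

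- **No count is stated.** The plan says that names are listed, not that they are counted, and the form itself is not in the documents. It may already record relationship. This stands: the count in the illustration is an assumption. But a summary by number, by having anyone at all or by composition would meet the same undefined question.
- **No analysis is named for secondary outcomes.** This stands, and it keeps the point away from the main conclusions. The commitment to report all results with significance and effect sizes still makes a T0 to T1 comparison likely.
- **Some participants may already know these people at T0.** They are recruited through the partner organisations, Peer Supporters make outreach visits to find hidden cases, and a social worker employed by the organisations conducts T0. This would shrink the artefact; only coding at both visits can show by how much.
- **Effect sizes would expose a trivial change.** A standardised change of about 0.05 would look negligible beside a small p-value. This is fair for low naming shares and less so for higher ones.
- **Typical Day is much less exposed.** For completers the sessions have ended by T1, the question concerns a typical day, group CBT is named only for moderately severe symptoms, and the activity-scheduling plan is described after the discharge decision. Engaging older adults "through productive ageing activities and mental wellbeing self-management training" is a stated objective, so such activity may be an intended effect. This stands, and Typical Day is only a lesser point.

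**Conclusion.** The point holds as a gap in outcome definition. Whether programme-supplied people belong in the support-network outcome is undefined, the matched Peer Supporter is a current contact at T1 for those not yet discharged or referred, and neither the design nor the recorded data as described would separate that contact from a real change in network. The size is unknown. The 5% to 10% figure depends on the assumed SDs, a count of names and 3,000 completers; it shows that few participants would suffice for significance, not that a large effect is expected.

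A reader might go further in three directions that the documents do not support:

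- *That the gain would end when the service ends.* Nothing shows this. The accurate statement is that the trial could not tell.
- *That repeating the measure at T2 would show whether it persists after staff leave.* Peer Supporters are still involved through the exit period and conduct the T2 assessment, so staff have not left by then.
- *That the treatment and recovery goal questionnaire (primary outcome 7) has the same defect.* It covers social network, but asks about present, anticipated and desired states, is not described as a list of names, and as a primary outcome is measured at T2.

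The plan should be changed on this point, but the primary clinical outcomes are not in question.

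**What to change.** At T0 and T1, code each person named as programme-supplied (project social worker, Peer Supporter or other programme staff) or not. State a scoring rule, define the support-network outcome on non-programme names, and report the change with programme names included as a separate result. Coding at T0 as well captures staff whom participants already knew.

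For Typical Day, flag activities delivered by JoyAge and report the T0 to T1 change with and without them. This keeps an intended effect on activity visible. It concerns reporting only; the exit criterion stays as it is.

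The cost is one extra code per name or activity, with no additional visit. The reported change is likely to be less favourable, but it can be interpreted.

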## Data Analysis

For the main outcome measures of depressive symptoms/risks, wellbeing, and personal recovery, repeated measures analysis and growth curve modeling with three time points will be applied. All results will be reported with the appropriate effect sizes, along with statistical significances and confidence intervals.

To evaluate cost-effectiveness and sustained cost-effectiveness, cost-utility analysis will be used for analyzing data at different time-points. We focus on the quality-adjusted life year (QALY), a generic measure of health, like a currency which combines the quality of life and duration of the quality of life (Luyten, Naci, & Knapp, 2016). It not only captures observable health outcomes but also reflects the subjective appraisals of how bad it is to experience these outcomes from participants' perspective. Findings of cost-utility analysis will be reported as an incremental cost-utility ratio (ICUR),

indicating that the incremental cost per QALYs gained. We will use STATA 14.0 (StataCorp, 2015) for data analysis.

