# Methods

#### Design

This intervention study is designed as a prospective, open-labelled, single-arm trial. In the one-group pretest-posttest design, data will be collected at the baseline (T0), after completion of the intervention (T1), and after completion of the exit-plan (T2).

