### **Assessment Procedures**

After basic screening, baseline evaluation (T0/intake) will be performed by trained social worker employed by NGOs and clinical information will be used for triage. After completion of the intervention or drop-out, a progress review evaluation (T1/review) will be done by social worker as well, and a client is discharged if he/she meets the exit criteria at T1. For dischargeable client, a 2-month exit plan will be provided, and he/she will be assessed at the end of the exit period (T2/exit) by Peer Supporters, specifically on progress in personal goals of recovery.

Assessment will last for around 60 minutes for all participants at T0 and T1, and for around 30 minutes at T2 for those who are eligible for discharge.

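### An incremental cost-utility ratio is promised from a single-arm trial, and no comparator is named for the cost and QALY increments

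*Combined protocol and SAP*

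**What the plan says.** Objective (e) is: "To establish evidence of the effectiveness and cost-effectiveness of JC JoyAge Phase II model". The Design section states: "This intervention study is designed as a prospective, open-labelled, single-arm trial". Assessments are planned at T0, T1 and T2.

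Data Analysis sets out the economic work: "To evaluate cost-effectiveness and sustained cost-effectiveness, cost-utility analysis will be used for analyzing data at different time-points". It continues: "Findings of cost-utility analysis will be reported as an incremental cost-utility ratio (ICUR"), explained as the added cost for each QALY gained. Under Measurements, QALYs come from local health utilities and duration, with EQ-5D-5L as the fifth primary outcome. Costs come from a short adapted service-receipt inventory (CSRI) and from health-service records.

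On T2, Measurements limits the visit to the primary outcomes, a list that includes EQ-5D-5L. Assessment Procedures says T2 is done "by Peer Supporters, specifically on progress in personal goals of recovery" and lasts "for around 30 minutes at T2 for those who are eligible for discharge". Those clients are the ones who met the exit criteria at T1: "For dischargeable client, a 2-month exit plan will be provided". For wellbeing, Data Analysis says that "repeated measures analysis and growth curve modeling with three time points will be applied".

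**The concern.** The reported measure claims a property that the design does not supply. To be incremental, a cost-utility ratio needs the costs and QALYs of an alternative, and the trial observes only people offered the programme. If T0 silently serves as the alternative, the ratio credits the programme with everything that happens after enrolment, including any recovery or deterioration that would have occurred anyway.

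Objective (e) is about cost-effectiveness, and Background expresses the hope that the model will be taken into regular services. A reader weighing that decision could take a before-after ratio as value for money against no programme. If T2 utilities feed the sustained result, the reader could also take a finding in discharged clients as applying to all participants.

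**Working it through.** The plan gives no target ratio, expected utility gain or cost figure, so there is nothing of its own to reproduce. The check is a reading of the text followed by an illustration.

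**1. Is there a comparator?** The ratio is (C1 - C0)/(Q1 - Q0), where 1 is the programme and 0 the alternative. Possible sources for C0 and Q0:
- Design: one group, measured before and after. None.
- Interventions: speaks of an intervention group, but no other group is described anywhere.
- Background: cites the earlier phase as evidence that the model works, not as a source of comparison costs or QALYs.
- Measurements: describes cost and utility data for participants only.
- Data Analysis: mentions different time-points, but does not say what the increments are measured against.

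**2. What would T0 supply?** A single visit gives a utility level, u0. A QALY is utility over time, so Q0 = u0 x L over a horizon L only if u0 is assumed to persist. In the same way, C0 = c0 x L needs a T0 service-use rate, c0, carried forward. Neither assumption is stated. Under Participants, people are enrolled because they have depressive symptoms, so some change without the programme is plausible.

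**3. Illustration (f is assumed; the documents give no value).** Let f be the share of the before-after QALY gain Q that would occur without the programme, with incremental cost D unchanged. A negative f means that health would have worsened.
- Reported ratio = D/Q
- True ratio = D/((1 - f)Q)
- True / reported = 1/(1 - f)

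| f | calculation | true / reported |
|---|---|---|
| -0.2 | 1/1.2 | 0.83 |
| 0 | 1/1.0 | 1.00 |
| 0.2 | 1/0.8 | 1.25 |
| 0.5 | 1/0.5 | 2.00 |

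Service costs can also change without the programme. Let s be the apparent service saving divided by programme cost, and g the share of that change that would occur anyway. Then true / reported = (1 - (1 - g)s)/((1 - s)(1 - f)), which returns to 1/(1 - f) when g = 0. With f = 0 and g = 0.5 (assumed):
- s = 0.3 gives (1 - 0.15)/0.7 = 0.85/0.7 = 1.21
- s = -0.3 gives (1 + 0.15)/1.3 = 1.15/1.3 = 0.88

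The factors fall on both sides of 1. They show that the result depends on an unstated counterfactual, not how large the error is or which way it runs.

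**4. T2.** Measurements implies EQ-5D-5L at T2, while Assessment Procedures describes a visit focused on recovery goals. If utilities are collected, they come only from clients who met the exit criteria at T1. T2 is the only visit after T1, so reading sustained cost-effectiveness as a T2 result is a reasonable inference, though the plan does not say so. The three-time-point growth model for wellbeing could use T0 and T1 data from people without T2 under a missing-at-random assumption. Data Analysis does not link that model to the QALYs.

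**The case against.** The best reply is that the single-arm design is declared openly, so an informed reader will take T0 as the reference. This limits the harm, but it does not supply the carry-forward assumptions, and the word incremental still promises more than a before-after change. It is also fair to say that relabelling alone changes nothing of substance. What matters is the stated counterfactual, the stated limitation and the sensitivity table.

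Several stronger readings are tempting, and the documents do not support them:
- **T0 is the only contrast available.** T1 is also planned after drop-out, so completers could be compared with drop-outs, though with confounding. Health-service records might also cover use before enrolment.
- **The ratio flatters the programme.** Nothing in the documents fixes the direction.
- **The CSRI cannot yield a cost rate.** No recall period is given, but the short version is still to be developed, and current level of service may already mean a frequency.
- **All-participant costs will be divided by QALYs from discharged clients only.** No section plans this.
- **The exit criteria select directly on EQ-5D-5L.** The activity criterion under Secondary outcomes is a different construct from a health-problem dimension, and selection on utility is not shown.
- **Anyone not dischargeable at the first review is lost to T2.** Interventions allows stepping up or down after a round, with follow-up until discharge or referral, so some clients may reach T2 later.

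**Conclusion.** The comparator point holds with high confidence: one arm, an incremental ratio promised, and no comparator named from Background to Data Analysis. It should be corrected. The factors of 0.83 to 2.00 rest on assumed f between -0.2 and 0.5 and unchanged incremental cost. They illustrate sensitivity and do not estimate bias, whose size and direction remain unknown.

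The T2 point is secondary and held with moderate confidence. It depends on EQ-5D-5L being taken at T2 and on the sustained result being read there. If both hold, that result describes a group selected on T1 status. This does not affect T0 and T1, where the full assessment is planned for all participants.

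**What to change.** - **Data Analysis, comparator.** Do one of two things. Either name an external comparator and the source of its costs and QALYs, saying explicitly whether the earlier phase or any other group plays that role. Or report a before-after cost-utility ratio with its counterfactual stated: T0 utility and T0 service-use rate carried forward. In the second case, say that it is not an estimate against no programme, and make sure the short CSRI yields a rate per unit time.
- **Sensitivity table.** For the before-after ratio, vary separately the shares of the QALY gain and of the service-cost change that would have occurred anyway, including negative values.
- **Population.** Base the main ratio on all enrolled participants to T1, including drop-outs where observed.
- **T2.** Reconcile Assessment Procedures and Measurements on whether EQ-5D-5L is collected. Then either label the sustained result as applying to discharged participants, with costs restricted to the same people, or estimate it for all participants under a stated missing-data model. The second option needs a sensitivity analysis that both raises and lowers the T2 utility assumed for those without the visit.
- **Objective (e).** Word the conclusion to match what is estimated.

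The cost is wording in a few sections, one table, and one missing-data analysis if an all-participant T2 estimate is wanted. No extra arm, visit or recruitment is needed. The downside is a more cautious cost-effectiveness statement.
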